IGF-1 and Bone Loss in Women with Anorexia Nervosa

NCT # 01406444

Version Date: January 16, 2019

VI. Biostatistical Analysis

Experimental Endpoint

The primary endpoint will be PA spine BMD, and the primary analysis strategy will be to use a linear random effects model to estimate and test the effects of the three therapies on the study endpoints. The model that we propose is one where each patient has a linear trajectory from baseline to 6 months and then a possibly different linear trajectory from 6 months to a year. The 3 parameters that describe this trajectory are the intercept at baseline, the first slope, and the second slope. We assume that these three parameters have a multivariate normal distribution, with means dependent on the treatment group, the parameters of which we will estimate using SAS PROC MIXED. Since there are two slope parameters that depend on treatment, the mean slope in the first period and the mean slope in the second period, it is necessary to define the contrast of these parameters that will be used as the primary test of treatment effect. The contrast we will use will be the one that estimates the difference in the change in the endpoint at 12 months between the treatment groups. The advantage of using this analysis method rather than an analysis of covariance using only the 12 month and baseline data is that the method we propose will be more powerful and will also accommodate missing data better. It will give unbiased estimates whenever data are missing at random, while last observation carried forward (LOCF) or a complete case analysis would be biased (89). We will examine goodness of fit to this model using tests based on adding quadratic terms and by residual plots. If necessary we will add higher order terms to the model. We would use LOCF or complete case analysis as a secondary analysis. We use a model which has a break point at 6 months for all patients even for those on continuous therapy (placebo, risedronate) because having models that differ for the 3 treatments requires strong assumptions that lead to biases (90). An additional advantage of this model is that it is relatively easy to add baseline covariates. The primary analysis would be intent to treat. Patients who wish to stop therapy will be encouraged to return for all evaluations. Our primary comparison for BMD is PA spine BMD, and other comparisons are considered secondary. In this way, we avoid having to correct each comparison using a multiple comparison correction such as the Bonferroni inequality. We consider the comparison of sequential therapy to risedronate and the comparison of each of these to placebo to be separate scientific questions, so we do not plan to correct these 3 planned contrasts using a multiple comparison procedure (91).

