
Markers of bone metabolism

The analysis will focus on 2 periods – one from 0 to 6 months, where we will have 2 post-treatment measurements, and one from 6 to 12 months, where we will also have 2 post-treatment measurements. The primary analysis will be to compare the bone markers in patients post risedronate values to the post-rhIGF-1 values using a repeated measures analysis of covariance where the covariant is the baseline value for each period and the primary question is on average over the period whether there is a difference in markers. The significance of the analysis in the first period is whether these markers are affected differently by the 2 treatments, rhIGF-1 and risedronate. The second question, for the second period, is whether pre-treatment with rhIGF-1 changes the response to risedronate.

Muscle mass

Body composition parameters (thigh muscle mass, total, subcutaneous and visceral abdominal fat) by cross-sectional CT at 0, 6, and 12 months. The primary analysis of this measure will be by analysis of covariance with the 6-month measures as the dependent variable and the baseline measure as a covariate.

Bone microarchitecture and strength

There will be two analyses of these data, one comparing 6 months to baseline with an analysis of covariance, and one comparing 12 months to baseline. The first analysis isolates the effect of IGF-1 vs. risedronate and placebo. The second measures the effect of the sequential therapy.

Power Analyses: Determination of an n of 100 subjects for the primary aim.

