The primary aim of the study is Specific Aim 1A, and the primary endpoint will be PA spine BMD. This aim will compare rhIGF-1 followed by risedronate (for anabolic consolidation and further BMD increases) to risedronate alone and to placebo. The study will determine 1) whether sequential therapy is superior to risedronate, 2) whether sequential therapy is superior to placebo and 3) whether risedronate administration is superior to placebo. A total of 100 patients will enter this three treatment parallel-design study. With 36 evaluable patients in each of the two active treatment groups (assuming a 10% drop-out rate), the probability is >80% that the study will detect a difference between sequential therapy and risedronate at a two-sided 5% percent significance level, if the true difference between the treatments is 2.5%. This is based on the assumption that the SD of the response variable (BMD in women with AN receiving oral contraceptives) is 2.69%, as we found in our previous study (24) and on the 2.5% difference we found in our interim analysis of our preliminary study of sequential rhIGF-1 followed by risedronate (4.8%) compared with risedronate alone (2.3%) at 12 months. In addition, it is consistent with the increase of 2.54% from baseline (3.05% compared with placebo) at the PA spine at 6 months in subjects who received rhIGF-1 and OCPs (see Background and Figure 1). Risedronate increased BMD at 6 months followed by a decrease of 0.3% between 6 and 12 months (see Progress Report). Thus, we expect that the principal difference between sequential therapy and risedronate alone will be the 6-month effect we found of rhIGF-1 in this estrogen-treated population of 2.54% plus 0.4%. With 36 subjects in each treatment group and 18 subjects in the placebo group (assuming a 10% drop-out rate), we expect the difference between the rhIGF-1 followed by risedronate and placebo groups to be approximately twice that between the two treatment groups and therefore we will have adequate power even though we have half the number of subjects in the placebo group. The power for this comparison will be 89%. We also have >80% power to detect a difference between the risedronate and placebo groups. These sample size estimates were based on using an analysis of covariance as the analysis method. The power calculated with this method will be somewhat less than the power achieved using the random effects model we propose.

Markers of bone metabolism

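### The SAP leaves open whether the primary BMD model has one baseline mean or one per arm; stating a common baseline mean is a cheap, modest improvement.

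*SAP*

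**What the plan says.** The SAP (section VI, Experimental Endpoint) models each woman's BMD as two straight segments joined at 6 months, with three random parameters: the baseline level and a slope for each half-year. Of these it says: "We assume that these three parameters have a multivariate normal distribution, with means dependent on the treatment group". Taken literally, that includes the baseline level. The sentence that follows begins differently: "Since there are two slope parameters that depend on treatment, the mean slope in the first period and the mean slope in the second period". The baseline level is not mentioned there.

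The primary test is defined by a contrast: "The contrast we will use will be the one that estimates the difference in the change in the endpoint at 12 months". Compared with an ANCOVA of 12-month on baseline values, the SAP says that "the method we propose will be more powerful and will also accommodate missing data better". On covariates it says only this: "An additional advantage of this model is that it is relatively easy to add baseline covariates". Baseline BMD is not named as one.

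Under Power Analyses the SAP states: "These sample size estimates were based on using an analysis of covariance as the analysis method". It adds that the random effects model will have somewhat more power than that. Elsewhere it adjusts for baseline explicitly. Bone markers use the baseline of each period as covariate, and muscle mass uses "analysis of covariance with the 6-month measures as the dependent variable and the baseline measure as a covariate".

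**The concern.** The two adjacent sentences lead to different primary models. One has nine free means (three arms by three visits). The other has seven, because randomised arms share one baseline mean. They give different estimates and p-values from the same data, and a primary analysis should not leave that choice to the programmer.

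The literal version also fits poorly with the SAP's own argument. A separate baseline mean per arm gives up the adjustment that ANCOVA makes, yet the sample size rests on ANCOVA and the model is presented as an improvement on it. At stake are some precision in all three planned contrasts and the part of a chance baseline difference that carries into the 12-month contrast. Both matter most against the small placebo arm.

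**Working it through.** **Inputs from the documents.** SAP, Power Analyses: 36, 36 and 18 evaluable; SD of response 2.69%; difference 2.5% for sequential therapy versus risedronate; two-sided 5%. Protocol, Baseline Visit: BMD at baseline, 6 and 12 months.

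**Inputs not in the documents.** The baseline SD as a percentage of the mean (S0) and the correlation of baseline with change (r). I take S0 from 3% to 15% and assume equal BMD variance at baseline and month 12. I read 2.69% as the SD of percent change before baseline adjustment; the SAP does not say which it is.

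**Step 1: the plan's own figures (normal approximation).**
- 36 v 36: SE = 2.69 × √(2/36) = 0.634. Then 2.5/0.634 − 1.96 = 1.98, so power is 97.6% (97.3% by noncentral t). The stated >80% holds.
- 36 v 18: SE = 2.69 × √(1/36 + 1/18) = 0.777. A 2.5% difference gives 89.6% (88.5% by noncentral t), close to the stated 89% for sequential therapy versus placebo. The difference of about twice 2.5% in the same paragraph would give over 99.9%. That mismatch is a separate matter; here I use 2.5% at 36 v 18.

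**Step 2: what each model estimates.** With three visits and a break at 6 months, the mean model is saturated within each arm. With complete data and free baseline means, the fitted means are the sample means, so the contrast is the plain difference in mean change. With one common baseline mean, the 12-month means are regressed on baseline and the contrast is the ANCOVA estimate. A simulation (6,000 replicates, 40/40/20 entered, assumed 6-month change SD 2.2%) agreed. At S0 = 3% the complete-data SEs for sequential therapy versus risedronate were 0.597 for free means and for the change score, and 0.543 for the common mean and for ANCOVA.

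**Step 3: size of the gain.** With equal variances, r = −2.69/(2 × S0), and the adjusted SD is 2.69 × √(1 − r²). The shift from a one-SE chance baseline difference is |r| times the unadjusted SE. Power is for a 2.5% difference.

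| S0 | r | r² | Adjusted SD | Power 36 v 36 | Power 36 v 18 | Shift 36 v 36 | Shift 36 v 18 |
|---|---|---|---|---|---|---|---|
| unadjusted | – | – | 2.69 | 97.6% | 89.6% | – | – |
| 3% | −0.45 | 0.201 | 2.405 | 99.3% | 95.0% | 0.28 | 0.35 |
| 5% | −0.27 | 0.072 | 2.591 | 98.4% | 91.7% | 0.17 | 0.21 |
| 8% | −0.17 | 0.028 | 2.652 | 97.9% | 90.4% | 0.11 | 0.13 |
| 12% | −0.11 | 0.013 | 2.673 | 97.8% | 90.0% | 0.07 | 0.09 |
| 15% | −0.09 | 0.008 | 2.679 | 97.7% | 89.8% | 0.06 | 0.07 |

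**Step 4: simulated variance ratio, common over free baseline mean** (sequential v risedronate; sequential v placebo).
- S0 = 3%: 0.83; 0.80 with complete data, and 0.82; 0.83 with about 10% missing at month 12.
- S0 = 5%: 0.94; 0.94 complete, and 0.95; 0.94 with missing data.
- S0 = 12%: 1.00; 1.00 complete, and 0.995; 0.999 with missing data. Estimating the baseline slope uses up a gain near 1%.

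**Step 5: the claim of more power than ANCOVA, about 10% missing, sequential v risedronate.** SEs for free baseline means against complete-case ANCOVA were 0.624 v 0.569 at S0 = 3%, 0.620 v 0.608 at 5%, and 0.630 v 0.633 at 12%. The literal model is ahead only in the last case, and barely. The common-mean model had the lower SE than ANCOVA in all three (0.566, 0.603, 0.629).

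**The case against.** The strongest reply is that the SAP may already intend a common baseline mean. The second sentence names only the slopes, and the power claim makes better sense that way. This stands. A reader of the first sentence alone might infer that the primary analysis is definitely unadjusted, and the documents do not settle that.

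A reader might also infer that free baseline means bias the contrast. They do not. Randomisation makes the difference in mean change unbiased, and all the estimators simulated were unbiased over randomisations. Only the shift given a particular chance imbalance is removed. Nor is baseline ignored in the literal model, since each woman's own value is subtracted.

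A third tempting step is to assume a large r alongside a wide baseline spread. At S0 = 12%, r = −0.3 or −0.4 would require BMD variance to fall within a year from 144 to about 132 or 125 (144 − 2 × 0.3 × 12 × 2.69 + 2.69² = 131.9, and likewise 125.4). The documents give no evidence of this. Regression to the mean is conceivable, because entry requires a low BMD score and a screening scan can serve as baseline, but its size is unknown.

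Finally, the 36 v 18 shifts should not be judged against the sequential-versus-risedronate difference. For sequential therapy versus placebo the SAP expects about 2 × 2.5 = 5%, so a one-SE shift of 0.09 to 0.35 is about 2-7% of it. For risedronate versus placebo it states no effect size.

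**Conclusion.** The point holds as a gap in specification with a modest efficiency cost on one of its two readings. On the literal reading the claim of more power than ANCOVA is unsupported for complete data whenever baseline BMD correlates with change. A common baseline mean removes the ambiguity and makes the claim consistent with the power basis.

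Under stable variance, the saving ranges from nothing measurable at a baseline SD of 12% to about a fifth of the variance at 3%. The sequential-versus-risedronate comparison is well powered under either model, so the practical benefit, if any, lies in the placebo contrasts. Both models are valid. I rate this a free, minor improvement. Its size depends on S0 and r, which the documents do not give, and on reading 2.69% as an unadjusted SD of change.

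**What to change.** In the SAP, section VI, Experimental Endpoint, replace the statement on the three means with: the means of the two slopes depend on treatment group, and the baseline mean is common to the three randomised arms (constrained longitudinal model). Keep the 12-month contrast as defined. In PROC MIXED, omit the treatment main effect at baseline and keep the treatment-by-slope terms.

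The constraint is justified because the protocol places DXA at the screening or baseline visit and randomisation at the baseline visit. The cost is one sentence and one model term, settled before unblinding, with no new data. If BMD tracks so closely that r is near zero, precision is essentially unchanged.

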## **RESEARCH DESIGN AND METHODS**

Briefly describe study design and anticipated enrollment, i.e., number of subjects to be enrolled by researchers study-wide and by Partners researchers. Provide a brief summary of the eligibility criteria (for example, age range, gender, medical condition). Include any local site restrictions, for example, "Enrollment at Partners will be limited to adults although the sponsor's protocol is open to both children and adults."

**Subjects:** Over the proposed 5 years, 200 women with AN will be recruited for an evaluable population of 90 women, 18-45 years old (assuming a 10% drop-out rate based on our previous studies). Subjects with AN will be randomized 2:2:1 in a double-blind fashion for 12 months: 1) sequential therapy with rhIGF-1 [REDACTED] for 6 months followed by 6 months of risedronate [REDACTED], 2) risedronate [REDACTED] or 3) double-placebo to determine effects on BMD, bone microarchitecture, and bone strength at trabecular and cortical sites. All subjects will meet the DSM-V criteria for AN and will be assessed for study suitability and monitored throughout the grant period for their overall psychiatric clinical state in coordination with the patients' clinical care team by a study psychiatrist, psychologist or psychiatric nurse practitioner. A standard oral contraceptive pill [REDACTED] or a standard transdermal estrogen patch [REDACTED] will be offered to potential subjects who are otherwise eligible to participate in the study but who are not currently receiving estrogen orally, transvaginally, or transdermally, nor have had their menses in the past two to three months. This medication will be prescribed at the lowest effective dose and for the shortest duration of time possible. Oral contraceptives or an estrogen patch will not be offered to any potential study participant with absolute or relative contraindications to estrogen use. We will not prescribe unopposed estrogen to any participant with an intact uterus. For such women who are not already receiving a progestin, we will concurrently provide [REDACTED] [REDACTED] [REDACTED]

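### Secondary bone-marker analysis: the second-period ANCOVA cannot show whether prior rhIGF-1 alters the response to risedronate, because prior rhIGF-1 is confounded with time on risedronate and with stopping rhIGF-1

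*SAP*

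**What the plan says.** The SAP (Markers of bone metabolism, analysis section) splits follow-up into months 0 to 6 and 6 to 12, with two post-treatment measurements in each. Each period is analysed "using a repeated measures analysis of covariance where the covariant is the baseline value for each period". The first period asks "whether these markers are affected differently by the 2 treatments, rhIGF-1 and risedronate". For months 6 to 12 it says: "The second question, for the second period, is whether pre-treatment with rhIGF-1 changes the response to risedronate".

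The Protocol (Research Design and Methods) gives the sequential arm rhIGF-1 "for 6 months followed by 6 months of risedronate". The other arms are risedronate and double placebo, all for 12 months, and the SAP (Experimental Endpoint) describes these two as continuous therapy. Markers are scheduled at months 1, 3, 6, 9 and 12.

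For microarchitecture the SAP takes another route. It plans two analyses, "one comparing 6 months to baseline with an analysis of covariance, and one comparing 12 months to baseline", and says of the 12-month one: "The second measures the effect of the sequential therapy".

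**The concern.** The second-period question concerns effect modification: does earlier rhIGF-1 change what risedronate then does to the markers? Answering it needs patients at the same stage of risedronate treatment who differ only in whether they had rhIGF-1 before. The two arms compared are at different stages, and one of them has just stopped rhIGF-1.

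The covariate is a separate difficulty. If it is the month-6 marker, it is an outcome of the first-period treatments, and the first-period analysis exists to test whether those treatments move the markers differently.

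A significant second-period result could therefore be reported as an effect of rhIGF-1 pre-treatment when it may reflect the stage of risedronate treatment, the withdrawal of rhIGF-1, or the adjustment for month 6.

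**Working it through.** **1. What each arm receives**

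| Arm | Months 0-6 | Months 6-12 |
|---|---|---|
| Sequential | rhIGF-1 | risedronate, first six months |
| Risedronate | risedronate, first six months | risedronate, second six months |
| Double placebo | placebo | placebo |

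In months 6 to 12 the first two rows differ in three ways at once: prior rhIGF-1, time on risedronate and recent withdrawal of rhIGF-1. No row starts risedronate at month 6 without rhIGF-1. The placebo row could show a time trend but not the difference between early and late risedronate. This step needs no assumed number.

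**2. Which covariate**

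The SAP does not write month 6, but that is the natural baseline of a 6-to-12-month period. The visit count fits: five scheduled marker visits against four counted post-treatment measurements leaves one over, as would happen if month 6 served as a baseline.

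**3. The plan's own marker figures** (SAP, Power Analyses, Markers of bone metabolism)

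Inputs: 76 evaluable patients, so 38 per arm; covariance matrices (350, 360; 360, 535) for PINP and (0.05, 0.012; 0.012, 0.049) for CTX.

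- PINP: variance of the mean of two visits = (350 + 535 + 2×360)/4 = 401.25, SD 20.03. Detectable difference at 80% power = (1.96 + 0.84)×sqrt(2×401.25/38) = 12.9, against a stated 13. Reproduced.
- CTX: variance of the mean = (0.05 + 0.049 + 2×0.012)/4 = 0.03075. Detectable difference 0.113 at 80% power and 0.130 at 90%. The stated 0.13 carries no power figure.
- Between-visit correlations: PINP 360/sqrt(350×535) = 0.83; CTX 0.012/sqrt(0.05×0.049) = 0.24.

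**4. What the month-6-adjusted contrast estimates**

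Let d be the true difference between regimens at months 9 and 12, g the difference between arms at month 6, and rho the within-patient correlation, with equal variances and a common correlation across visits. The within-arm slope of mean(9, 12) on month 6 is then rho, and

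adjusted contrast = d - rho×g.

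Adjusting for month 0 gives d, because randomisation makes the expected month-0 gap zero. Illustrative shifts with d = 0:

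| Marker | Assumed g | rho | Shift = -rho×g |
|---|---|---|---|
| PINP | 13 | 0.5 | -6.5 |
| PINP | 13 | 0.83 | -10.8 |
| CTX | 0.13 | 0.24 | -0.03 |

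The reverse also holds: if d = rho×g, a true PINP regimen difference of 10.8 (rho 0.83) is estimated as about zero. The shift does not depend on sample size.

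**5. Precision of the month-0 alternative**

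Under the same structure, the correlation of month 6 with mean(9, 12) is r6 = rho/sqrt((1 + rho)/2). If month 0 explained nothing, its interval would be 1/sqrt(1 - r6²) times as wide: 1.05 (rho 0.24), 1.22 (rho 0.5) or 2.02 (rho 0.83). These are upper figures. They ignore the month-6 gap, which would itself widen the month-6-adjusted interval, and the loss vanishes if month 0 predicts as well as month 6.

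**The case against.** - **The month-6-adjusted ANCOVA is a legitimate conditional analysis.** Naming the covariate implies the null: equal expected months 9 and 12 values for patients with the same month-6 value. In simulation it rejects at 5% under that null. This stands, and the plan cannot be faulted for leaving its null unstated. But that null is neither the pre-treatment question nor a randomised comparison of regimens.
- **The regimen comparison may already be intended.** The marker power section sizes a CTX difference between sequential therapy and risedronate over 12 months, with a baseline covariate and two post-baseline measurements. One reading of this is months 9 and 12 adjusted for month 0. That is fair, but the analysis section does not define that comparison, so the two sections need to be aligned.
- **Each arm's risedronate response could be measured from its own pre-risedronate baseline**, setting sequential months 6-12 against risedronate months 0-6. The SAP's loose wording about values after each drug leaves some room for this, and it would match time on drug. However, the question is tied to the second period, the comparison would not be concurrent, and rhIGF-1 withdrawal would remain in it.
- **The analysis is secondary.** Bone markers appear in neither Specific Aim. This stands and limits the weight of the point.

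**Conclusion.** The inference the SAP attaches to the second-period marker ANCOVA cannot be drawn in this design. That rests on the treatment sequences alone. The second part, that the adjusted contrast is not a randomised comparison of regimens, rests on reading the period baseline as month 6. Its size is about -rho×g, and the documents give neither the month-6 gap nor the correlation across the drug switch. The gaps used above are the SAP's detectable differences (the CTX one is stated over 12 months). The correlations 0.83 and 0.24 come from pilot patients on risedronate only or double placebo, and 0.5 is illustrative. For CTX the shift is small.

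Two stronger readings are tempting and not supported:

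- A reader might infer a badly inflated false-positive rate. With 38 per arm, the gaps above and equal true levels at months 9 and 12, simulated rejection is 43% and 99% for PINP and 12% for CTX. But in that scenario the arms do change differently after month 6, so rejection is not an error for a question about response. These figures also depend on the assumed gap.
- A reader might take the pilot statement "Risedronate increased BMD at 6 months followed by a decrease of 0.3% between 6 and 12 months" as proof that time on risedronate drives the contrast. It concerns BMD, not markers, and is a within-arm change with no matching placebo change by period. The documents give no marker change by period.

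The SAP should be changed on this point. The primary PA spine BMD contrast is unaffected.

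**What to change.** 1. Replace the sentence on rhIGF-1 pre-treatment with a statement that the second-period contrast cannot separate pre-treatment from time on risedronate and rhIGF-1 withdrawal.
2. Specify in the marker analysis section a comparison of sequential therapy with risedronate at months 9 and 12, by repeated measures ANCOVA with the month-0 marker as covariate, interpreted as a comparison of regimens. This agrees with the 12-month microarchitecture analysis and with the 12-month CTX comparison in the power section. It does not answer the pre-treatment question, and the text should say so.
3. Keep the month-6-adjusted analysis as exploratory, with its null written out.

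Cost: SAP wording. The month-0 marker is already needed as the baseline of the first-period analysis. The interval may be wider, by at most the factors in step 5 of the working. If month 0 explains nothing and the SAP's matrices are unadjusted, the detectable differences are 12.9 PINP and 0.113 CTX with 38 per arm (13.2 and 0.116 with the 36 per arm used for the primary aim). If the matrices are already baseline-adjusted, which the SAP does not say, dividing by sqrt(1 - r²) gives 14.9 and 0.130 at an assumed baseline correlation r of 0.5, or 18.0 and 0.158 at 0.7. These could exceed the SAP's 13 and 0.13.

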With 76 evaluable patients randomized between risedronate and rhIGF-I for the first six months, we will have an 80% chance of detecting a difference of 13 units in PINP. This represents a difference of 25% of the baseline value of PINP in patients with AN. For the difference between these groups (sequential therapy and risedronate) over the 12-month period, we will be able to detect a difference of 0.13 units in CTX at a 5% significance level. For CTX, the difference is 19% of the baseline level. The power calculation was based on a repeated measures analysis of covariance with the baseline value as a covariate and two post baseline measurements. We used the programs provided by [REDACTED] (92). The variance covariance matrix of the measurements were (350,360;360,535) for PINP and (0.05,0.012;0.012,0.049) for CTX and are from our pilot study with 36 patient completers in the risedronate only and double placebo groups.

Muscle mass

With 40 women in the rhIGF-1 group and 20 in the placebo group, the probability is 80% that the study will detect a treatment difference at a two-sided 5.0% significance level, if the true difference between the treatments is 4.3%. This is based on the assumption that the SD of the response variable is 5.2%, as we found when we examined the 6-month change from baseline in women of reproductive age receiving placebo (93). We conclude that this is feasible because it is smaller than the 6% change in fat-free mass that was produced by IGF-1 in our previously published study in patient with AN (24).

GH and IGF-1

With 40 women in the rhIGF-1 group and 20 in the placebo group, the probability is 80 percent that the study will detect a treatment difference at a two-sided 5.0% significance level, if the true difference between the treatments is 0.7 times the SD of change from baseline.

Bone microarchitecture: Spine

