The literature on trabecular thickness uses percent change as the unit of effect. With 36 evaluable patients in each treatment group the 95% confidence interval on the change in trabecular thickness of the spine will be 2.7% for each of the two active treatments based on Graeff *et al.* who estimated the difference between two spine microarchitectural endpoint measurements 12 months apart to be 8.8%, depending on the measure, and the SD of the change of 8.2% (73). Based on this we will be able to estimate trabecular thickness at the spine to sufficient precision to be confident as to whether the treatments affect this variable.

Radius and Tibia

With 40 patients in each treatment group and 20 in the placebo group entering the study and a 10% drop-out rate, the probability is 80 percent that the study will detect a treatment difference at a two-sided 5.0% significance level, if the true difference between the treatments is 2%. This assumes that the within subject SD is 3%, which is the interscan variation described for the instrument (94). If the within patient SD is twice this, e.g. 6%, we would be able to detect a change in trabecular thickness of 4%, which is smaller than the difference between women with and without fractures of 6% (95). In addition, for both of the comparisons with placebo, we will be able to detect a 2.5% difference between groups with an 80% probability. If the within patient SD is twice this, we would be able to detect a change in trabecular thickness of 5%. Thus, we think that this measurement has the potential of detecting small clinically important differences in this parameter. The SD of 6% is greater than the SD found in the EUROFORS study using similar high-resolution CT scanners after 6 months of treatment with PTH of 5.6% (73). In the powering, we focus on the pairwise comparisons of the treatment arms because the scientific questions are distinct for each pairwise comparison.

Bone strength (FEA)

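### The bone-marker power paragraph counts 76 evaluable patients where the plan's own figures give 72; PINP power slips from about 80% to about 78%, and CTX has no stated power

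*SAP*

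**What the plan says.** The SAP (section VI, Power Analyses, Markers of bone metabolism) starts from "With 76 evaluable patients randomized between risedronate and rhIGF-I for the first six months" and concludes "we will have an 80% chance of detecting a difference of 13 units in PINP", which it equates to 25% of baseline. It then turns to the same two groups over 12 months and says "we will be able to detect a difference of 0.13 units in CTX at a 5% significance level", equated to 19% of baseline. That second sentence gives neither a power nor a separate sample size. The paragraph supplies a 2 by 2 covariance matrix for each marker and names the method: a repeated-measures ANCOVA adjusting for baseline, with two later values per patient.

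Elsewhere the numbers are these:

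- SAP, power for the primary aim: "With 36 evaluable patients in each of the two active treatment groups (assuming a 10% drop-out rate", out of 100 patients entered.
- SAP, power for radius and tibia: "With 40 patients in each treatment group and 20 in the placebo group entering the study and a 10% drop-out rate".
- SAP, spine microarchitecture and FEA: 36 evaluable per treatment group.
- Protocol, Research Design and Methods: "200 women with AN will be recruited for an evaluable population of 90 women, 18-45 years old (assuming a 10% drop-out rate", and "Subjects with AN will be randomized 2:2:1 in a double-blind fashion for 12 months".

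**The concern.** Evaluable is the word the plan uses for patients left after drop-out, so 76 should be the two active arms after the stated 10% loss. It is not. It is also not the number entered, which is 80. A reader therefore meets two evaluable counts for the same two arms, and the larger one supports the marker power claim.

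The second difficulty is CTX. The only power in the paragraph is the 80% attached to PINP. A reader who carries it over to CTX finds that 0.13 does not follow from the SAP's own matrix. What is at stake is whether the stated sensitivity of the marker comparison matches the number of patients that the trial expects to have.

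**Working it through.** **Patient numbers.** 100 patients at 2:2:1 give 100 × 2/5 = 40 per active arm. With 10% drop-out, 40 × 0.90 = 36 per arm, or 72 in both. The Protocol agrees: 90 evaluable at 2:2:1 is 36/36/18. The marker figure of 76 is 38 per arm, and 76/80 = 0.95, a 5% loss.

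**Variance.** The SAP's marker analysis asks about the average over the period, so the relevant quantity is the mean of two post-baseline values, with variance (v11 + v22 + 2·v12)/4.

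- PINP, matrix (350, 360; 360, 535): (350 + 535 + 720)/4 = 401.25, SD 20.03.
- CTX, matrix (0.05, 0.012; 0.012, 0.049): (0.05 + 0.049 + 0.024)/4 = 0.03075, SD 0.1754.

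The matrices are treated as already adjusted for baseline, so no further gain from the covariate is taken. The test is two-sided at 5%; the CTX sentence does not give sidedness, and two-sided is assumed as elsewhere in the SAP.

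**Formulas (normal approximation).** SE = SD·√(2/n), with n per arm. Power = Φ(difference/SE − 1.96). Difference detectable with 80% power = (1.960 + 0.842)·SE. The t results below use the noncentral t distribution instead.

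**PINP at 76: the SAP's own figure.** SE = 20.03·√(2/38) = 4.595. Power at 13 units = Φ(2.829 − 1.960) = 80.8%; by t, 79.7%. The stated 80% reproduces. The calculation behind the SAP therefore appears to have used 38 per arm, so 76 is unlikely to be a typing slip.

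**PINP at 72.** SE = 20.03·√(2/36) = 4.721. Power at 13 units = Φ(2.753 − 1.960) = 78.6%; by t, 77.5%.

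**CTX.** At 76, SE = 0.1754·√(2/38) = 0.0402. At 72, SE = 0.1754·√(2/36) = 0.0413.

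| | 76 evaluable (normal / t) | 72 evaluable (normal / t) |
|---|---|---|
| PINP: power at 13 units | 80.8% / 79.7% | 78.6% / 77.5% |
| PINP: detectable at 80% | 12.9 / 13.0 | 13.2 / 13.4 |
| CTX: power at 0.13 units | 89.8% / 89.0% | 88.2% / 87.3% |
| CTX: detectable at 80% | 0.113 / 0.114 | 0.116 / 0.117 |
| CTX: detectable at 90% | 0.130 / 0.132 | 0.134 / 0.136 |

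So 0.13 is what 76 patients detect with 90% power under the normal approximation. Other readings of the CTX matrix do not yield 0.13 at 80% power with 76: a single time point, or a baseline/post pair, gives 0.138 to 0.144, and a change score gives 0.176 (all by normal approximation).

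**As a share of baseline.** The SAP's percentages imply baselines of 13/0.25 = 52 for PINP and 0.13/0.19 = 0.684 for CTX. At 72, the differences detectable with 80% power are 13.2/52 = 25.4% to 13.4/52 = 25.8% for PINP, and about 17% for CTX (0.117/0.684).

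**The case against.** *Retention may be better at six months.* The 76 is tied to the first six months, whereas the 36 per arm supports a 12-month BMD comparison. Fewer patients may be lost by month 6, and markers are drawn from month 1, so some later drop-outs would still contribute to a repeated-measures analysis. This is plausible for PINP. But the documents state no six-month loss rate, and the argument does not reach the 12-month CTX sentence, which gives no other sample size.

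*The SAP does not use 36 throughout.* Correct: muscle mass and GH/IGF-1 are powered on the full 40 and 20. Those sections do not call the numbers evaluable, however, and they do not explain 76.

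*The baseline covariate could recover the loss.* The documents do not say whether the matrices are already baseline-adjusted, and they give no correlation between baseline and later values. If the matrices are unadjusted, an assumed correlation between baseline and the two-value mean of about 0.19 (normal) to 0.25 (t) would restore 80% at 72. This stands as a limit on the PINP shortfall. Against it, the same gain would lift power at 76 above the stated 80%; the reading without further gain is the one that reproduces the SAP's figure.

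*The shortfall is close to rounding.* Also fair. Both 13.2 and 13.4 round to the SAP's whole-number 13, and the SAP's calculation used a program that cannot be inspected here.

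*Stronger readings.* A reader might infer that neither marker figure reproduces. The documents do not support that: PINP reproduces at its stated 76, and CTX carries no stated power to fail against. If 80% is carried over from the PINP sentence, 0.13 is larger than the trial needs to detect, so the error is on the cautious side.

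**Conclusion.** The inconsistency in the count stands: 76 evaluable against the plan's 72, with no stated 5% loss to account for it. Its effect is small. PINP power at 13 units is about 78% instead of 80%, a shortfall against the stated figure of 1.4 points (normal) to 2.5 points (t). That result rests on the average over two values being the quantity tested, on a two-sided 5% test, and on the matrix being already baseline-adjusted.

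For CTX the defect is an omission: the sentence does not state its power, and the difference it quotes is conservative. A reader might also take this as evidence that the trial is underpowered. It is not. Markers are secondary, and the primary BMD calculation already uses 36 per active arm.

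**What to change.** In the marker power paragraph:

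1. Replace 76 with 72 evaluable (36 per active arm). Alternatively, state and justify a 5% loss at six months for PINP only, and use 72 for the 12-month CTX comparison.
2. With 72, restate PINP as about 78% power at 13 units, or as 80% power at about 13.2 to 13.4 units (25% to 26% of baseline).
3. Attach a power to CTX: about 87% to 88% at 0.13 units with 72. If 80% is preferred, give about 0.116 to 0.117 units (about 17% of baseline).
4. Say whether the covariance matrices are already adjusted for baseline. If they are not, give the correlation and rerun the calculation.

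The cost is SAP wording only. The PINP statement becomes slightly less favourable, and enrolment, the primary sample size and the analysis do not change.
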